If significant abnormalities are identified during screening, these test results would be given to the subject, together with a recommendation regarding the appropriate type of follow-up (e.g., see family doctor or specialist).

The overall trial outcome would not be shared with individual participants or their providers but will be made accessible via scientific publication. Furthermore, data

obtained with the CogState test battery will be provided to Cogstate Ltd upon completion of the trial for their own research and development. No subject identifiers will be given to Cogstate Ltd. We may include age in years and gender.

ID: VIEW4E02808CBD800
Name: v2_Sharing of Results

View: v2_Research with Drugs or Biologics

Research with Drugs or Biologics

You indicated on the "Type of Research" page that your study involves use of unapproved drug(s)/biologic(s) or approved drug(s)/biologic(s) whose use is specified in the protocol AND/OR evaluation of food(s) or dietary supplement(s) to diagnose, cure, treat, or mitigate a disease or condition.

- 1 * List all drugs/biologics to be administered in this study. Be sure to list each drug/biologic with its generic name only.

Drug Name	FDA Approved	IND Number	PI IND Holder
-----------	--------------	------------	---------------

View: Nicotine polacrilex lozenge

yes

- 2 * Attach the drug package insert or investigational drug brochure for the drugs being administered in this study:
Package insert 12/10/2013 3:14 PM 12/10/2013 3:14 PM

- 3 If more than one drug is administered, discuss the risk implications of drug/therapy interactions:

- 4 * Will you be using Investigational Drug Services?

Yes No

ID: VIEW4E0916E6E1400

Name: v2_Research with Drugs or Biologics

View: v2_Drug or Biologic Storage and Handling

Drug or Biologic Storage and Handling

- 4.1 * Do you have a plan regarding access controls for essential and appropriate research personnel?

Yes No

- 4.2 * Will you have procedures for verifying physical access to the drug(s)?

Yes No

- 4.3 * Will you label the drug(s) so that it is (they are) used appropriately for the study?

Yes No

- 4.4 * Will there be an establishment of a drug transfer process both into and out of the research site?

Yes No

- 4.5 * Will the storage of the drug(s) be in a secure environment and include locks on doors and controlled access?

Yes No

- 4.6 * Do you have a plan for only allowing trained personnel to administer the drug(s)?

Yes No

- 4.7 If applicable, will the storage of the drug(s) be at the appropriate temperature, with a storage and temperature log?

Yes No

ID: VIEW4E1D85CC57C00

Name: v2_Drug or Biologic Storage and Handling

View: v2_Placebos

Placebos

- 1 * Is this study placebo controlled?

Yes No

ID: VIEW4E0514EECCC00
Name: v2_Placebos

View: v2_Placebo Use

Placebo Use

You indicated that this study is placebo-controlled.

If you uploaded a separate research protocol document in the 'Research Protocol' page, cite the applicable section

and page numbers from that document in the answer box below.

- 1.1 * **Justify the use of the placebo study design and how the benefit to society outweighs the risks to the participants:**
 All participants will receive 10 weeks of cognitive remediation training as part of the study, but only half of the participants will receive a nicotine lozenge biweekly prior to the training session. The other half will receive a placebo lozenge matched for looks and taste. There is no risk associated with receiving placebo instead of nicotine lozenges. If nicotine enhances the training effects, as hypothesized, then the placebo group on average will derive less benefit from the training. This remains to be shown, and it could not be shown without the placebo group. If it was shown to be true, this would provide the proof-of-principle for a mechanism that may help alleviate one of the most debilitating symptoms of schizophrenia.
- 1.2 * **Is the placebo being used in place of standard therapy?**
 Yes No
- 1.3 * **Is the standard treatment considered effective?**
 Yes No

ID: VIEW4E0514D79B400
 Name: v2_Placebo Use

View: v2_Psychological/Behavioral/Educational Methods and Procedures

Psychological/Behavioral/Educational Methods & Procedures

You indicated on the "Type of Research" page that your study involves a psychological/behavioral/educational method or procedure such as a survey, questionnaire, interview, or focus group.

- 1 * **Select all behavioral methods and procedures which apply to this study:**

Surveys/questionnaires
 Key informant or semi-structured individual interviews
 Individual or group behavioral observations
 Psychosocial or behavioral interventions
 Neuropsychological or psychophysiological testing

ID: VIEW4E09416F57800

Name: v2_Psychological/Behavioral/Educational Methods and Procedures

View: v2_Surveys/Questionnaires

Surveys/Questionnaires

You indicated that this study involves surveys and/or questionnaires.

If you uploaded a separate research protocol document in the 'Research Protocol' page, cite the applicable section and page numbers from that document in the answer boxes below.

- 1 * **List all questionnaires/surveys to be used in the study, including both standardized and non-standardized assessments:**
 Questionnaire asking about hours of sleep, caffeine and cigarette consumption today, to be used on each training day.
 Psychiatric and non-psychiatric medication forms, to record all currently taken medication
 Side-effects checklist to be used in the nicotine exposure session(s)
 The state- and the trait-version of the State-Trait Anxiety Inventory
 The Reasons for Smoking questionnaire
 The Nicotine Use Questionnaire
 The Nicotine Dependence Questionnaire
 A questionnaire recording the participant's guess as to whether or not their lozenges contained nicotine (Treatment Group Guess), to be completed with the outcome measurement immediately following training completion.
 A medical history pre-screening questionnaire, to be performed by a research assistant prior to the Medical History by the physician.

- 2 * **Upload a copy of all questionnaires/surveys:**

Name	Created	Modified Date
Medical history pre-screen	12/12/2013 3:22 PM	12/12/2013 3:31 PM
Treatment Group Guess	12/10/2013 4:15 PM	12/10/2013 4:15 PM
Nicotine Dependence Questionnaire	12/10/2013 4:02 PM	12/10/2013 4:02 PM
Nicotine Use Questionnaire	12/10/2013 4:01 PM	12/10/2013 4:01 PM
Reasons for Smoking Questionnaire	12/10/2013 4:01 PM	12/10/2013 4:01 PM
State-Trait Anxiety Inventory - Trait version	12/10/2013 4:00 PM	12/10/2013 4:00 PM
State-Trait Anxiety Inventory - State version	12/10/2013 4:00 PM	12/10/2013 4:00 PM
Side-Effects Checklist	12/10/2013 3:58 PM	12/10/2013 3:58 PM
Non-Psychiatric Medication Form	12/10/2013 3:57 PM	12/10/2013 3:57 PM
Psychiatric Medication Form	12/10/2013 3:56 PM	12/10/2013 3:56 PM
Sleep-Smoke-Caffeine Questionnaire	12/10/2013 3:44 PM	12/10/2013 3:44 PM

3 * What is the total length of time that each survey is expected to take?

Sleep-Smoke-Caffeine Questionnaire: 3 min

Medication forms: 10 min

Side Effects Checklist: 5 min

STAI - State: 4 min

STAI - Trait: 4 min

Reasons for Smoking Questionnaire: 3 min

Nicotine Use Questionnaire: 5 min

Nicotine Dependence Questionnaire: 5 min

Treatment Group Guess: 2 min

Medical history pre-screen: 5 min

4 * Are any of the questions likely to cause discomfort in participants or cause harm if their confidentiality were breached? (i.e., Illegal activities)

 Yes No

5 * Do any questions elicit information related to the potential for harm to self or others?

 Yes No

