- 1 * Provide a summary of the background and purpose of the study in language that can be understood by a person without a medical degree.

Schizophrenia is marked by problems in attention, memory and problem solving. These deficits predict long-term functional outcome such as the ability to live independently and maintain employment, but they are not ameliorated by currently available medications. Cognitive training improves these functions to some degree, but this approach is very time- and resource-intensive. The current project aims at enhancing and accelerating the benefits that people with schizophrenia derive from cognitive training by administering nicotine during some of the training sessions. This would provide the proof of principle for a treatment intervention that can improve cognitive symptoms of schizophrenia.

ID: VIEW4E02805CF7000
Name: v2_Lay Summary

View: v2_Justification, Objective, & Research Design

Justification, Objective, & Research Design

If you uploaded a separate research protocol document in the 'Research Protocol' page, cite the applicable section and page numbers from that document in the answer boxes below.

- 1 * Describe the purpose, specific aims, or objectives of this research. State the hypothesis to be tested:

The current project aims at determining whether the intermittent presence of nicotine during cognitive training exercises in people with schizophrenia will shorten the training period necessary to induce significant and clinically relevant improvement and enhance the improvement seen after a training period of specified length. Hypothesis 1a: Nicotine administration during training will increase the size of all measured effects of the training intervention, and will accelerate the time course of performance enhancement on the MCCB and training exercise progression parameters.

Hypothesis 1b: The larger training effects in the Nicotine Group will persist beyond the end of the intervention.

Hypothesis 2a: Within-session progress on the training exercises will be larger in the presence of nicotine than in the presence of placebo.

Hypothesis 2b: These acute nicotine-induced performance elevations will persist beyond the presence of nicotine through subsequent non-drug training sessions, giving evidence of an acute facilitation of learning processes.

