- 2 * Discuss the research design including but not limited to such issues as: probability of group assignment, potential for subject to be randomized to placebo group, use of control subjects, etc.:

Volunteers with a DSM-IV diagnosis of schizophrenia or schizoaffective disorder will be recruited, screened, and allocated in a double-blind manner to either the Nicotine Group or the Placebo Group. All participants will be asked to perform 10 weeks of cognitive remediation training (Posit Science, Duncan, SC), with daily training sessions Monday through Friday. On Mondays and Thursdays, all participants receive a lozenge 20 min prior to the training. In the Nicotine Group, the lozenge will contain 2 or 4 mg of nicotine, depending on smoking status. In the Placebo Group, the lozenge will be a matched placebo.

Outcome measures (OCMs) are assessed on Wednesdays in week 0 (day before training starts), weeks 4, 7 and 10 (after the training session), and week 14 (four weeks after training ends). OCMs are assessed on a non-drug day (Wed) because we are not studying the acute effects of nicotine but nicotine-induced enhancement of longer-term training effects.

- 3 * Describe the relevant prior experience and gaps in current knowledge. Describe any relevant preliminary data:

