Volunteers who provide Informed Consent will be screened for all Inclusion/Exclusion criteria. SCREENING will include: - Verification of age. - The SCID, to determine the presence/absence of current psychiatric conditions. For most patients, a SCID will have already been obtained and does not need to be repeated. - Medical history targeted at the cardiovascular, neurological, cognitive and other exclusion criteria. - Blood pressure and heart-rate reading. - ECG (12-lead with 3-5 minute rhythm strip). Exclusionary conditions documented on ECG include: Wolfe Parkinson White syndrome Myocardial ischemia and infarction Complete left bundle branch block PR interval <120 ms or >200 ms Prolonged QT interval (corrected) >500 ms Cardiac arrhythmias as defined by PACs >3 per min or PVCs >1 per min - Urine drug test, as a possible indication for substance abuse or dependence (may be repeated at any time during the study if intoxication is suspected) - Alcohol breathalyzer test, as a possible indication for alcohol abuse or dependence (may be repeated at any time during the study if intoxication is suspected) - Urine pregnancy test for females (also performed at the beginning of the cognitive training phase, and every two weeks thereafter) - Targeted questions about smoking history and motivation to stop smoking - Breath CO reading, as an indicator of smoking status and frequency - Listing of all currently taken medication - Vision test - The Addiction Severity Index - Drug and Alcohol Use subscale as an indicator for substance abuse or dependence. - The Wechsler Abbreviated Scale of Intelligence (WASI), as an indicator for possible mental retardation. Volunteers who pass the screening will be randomized to either the nicotine group or the placebo group. Randomization will be performed by the MPRC's biostatistician, [name], upon receiving a randomization request from the research assistant coordinating the study or a study investigator. Participants are then scheduled for a first NICOTINE EXPOSURE SESSION. In this session, participants will consume a nicotine lozenge (2 mg for non-smokers, 4 mg for smokers) if they have been randomized to the nicotine group and a placebo lozenge if they have been randomized to the placebo group. The number of smokers will be counterbalanced between the nicotine and placebo group. Participants will be instructed not to eat or drink within 15 min prior to or while consuming the lozenge. Participants are asked to report any adverse effects as soon as noted and to rate their subjective state immediately before the lozenge and every 30 min thereafter (see Side-Effects Checklist under "Additional Documents"). At this time, an investigator will also take their blood pressure and heart rate. The adverse effects of nicotine develop rapid tolerance. If any adverse effects are observed that are greater than "mild" and were not present pre-lozenge, the participant will undergo another lozenge exposure session on a separate day before starting the study. This may be repeated up to 4 times. Once both the participant and the investigator judge that any untoward effects of the lozenge are mild and tolerable and will not interfere with the cognitive training, the first outcome measurement session is scheduled, and the daily training sessions will commence the day after. A smoker who cannot tolerate the 4-mg lozenge may be dosed with a 2-mg lozenge in the cognitive training phase (the study would be single-blind for this subject). A participant who cannot tolerate the 2-mg lozenge even after repeated attempts will be excluded from the study. Participants who with the 2 mg lozenge display a rise in blood pressure by >20 mm Hg relative to pre-lozenge, a rise in HR to >120, or vomiting, will also be excluded from the study. OUTCOME MEASUREMENTS will be performed before the training begins, and approximately every 4 weeks after that until 4 weeks after the training ends. During the training phase, the outcome measurements will be performed AFTER completion of the daily cognitive training session. We will always schedule at least 1 hour between training and the outcome measurement, during which the participant can rest or have lunch. Outcome assessments are: a) The MATRICS Consensus Cognitive Battery (MCCB), an FDA-approved assessment tool for trials of cognition-enhancing treatments in PSZ. The battery measures 7 domains: speed of processing, attention/vigilance, working memory (verbal, nonverbal), verbal learning, reasoning, problem solving, and social cognition. b) The progression in training exercise parameters since the last outcome measurement time point (see below). c) Symptom assessments: the Brief Psychiatric Rating Scale, Scale for Assessment of Negative Symptoms, and Calgary Depression Scale. d) The state version of the State-Trait Anxiety Inventory. e) The Cogstate computerized assessment battery. Further outcome measures taken only pre- and post-training (week 0 and 10): a) Working Memory capacity (K) derived from a computerized change localization task. Two to four colored squares are shown for 100 ms. After a delay, they reappear and the task is to click on the one square that has changed color. b) The UCSD Performance-Based Skills Assessment, measuring ability to perform real-life tasks by standardized role-play. c) Quality of Life Scale, measuring functional outcome and quality of life in PSZ. d) The trait version of the State-Trait Anxiety Inventory. e) The Cognitive Assessment Interview (CAI), a brief interview-based measure of daily life cognitive functioning, administered to both the PSZ and a close relative or caretaker. The CAI was developed based on two longer scales and assesses 10 items related to working memory, attention/vigilance, learning/memory, problem solving, processing speed, and social cognition, with little or no repetition effects. f) Questionnaire asking each participant to guess their treatment group (nicotine or placebo; post-training only). g) A 5-ml venous blood sample will be taken, centrifuged, and frozen. At the completion of the study, the samples will be analyzed for TNF alpha, and potentially other inflammatory markers, to test whether repeated nicotine exposure may have anti-inflammatory effects that may be related to any effects on cognitive outcome measures. If a participant declines to have their blood drawn but are otherwise eligible for the study, they may participate without the blood draws. COGNITIVE REMEDIATION TRAINING PROCEDURE Prior to each daily training session, participants will complete a brief checklist about their caffeine and cigarette consumption today (how much/how many), when they last smoked/drank a caffeinated beverage, how many hours of sleep they got the previous night, when they last drank alcohol and how much. Prior to each session, smokers also provide a CO breathalyzer reading. Each training session will include ~30 min of auditory and ~30 min of visual training exercises by Posit Science, in a counterbalanced manner. The auditory training consists of six exercises: fast and accurate discrimination of (1) sound frequencies, (2) phonemes and (3) syllables, and recall of syllables, (4) sequences of syllables, (5) multi-element verbal instructions, and (6) details of a narrative. The visual training consists of five exercises designed to (1) improve visual precision, (2) increase capacity to divide visual attention, (3) improve visual memory, (4) expand field of view, and (5) increase visual processing speed. The programs train the fine-tuned and differentiated processing of sensory input and engage attention, working memory and/or executive processes. To induce the right level of challenge and promote engagement and motivation, task difficulty adjusts continuously to user performance to maintain ~85% correct responses (which are rewarded by auditory and visual feedback). Adjustable parameters include presentation time, interstimulus interval, physical similarity between stimuli, stimulus eccentricity, number of stimuli, and information complexity. Some exercises provide a progress summary of these parameters after each session. These values will be recorded on all training days. Other exercises provide a separate assessment tool to monitor progress. These assessments will be performed every 4 weeks with other outcome measurements. Every Monday and Thursday, a nicotine or placebo lozenge, encapsulated in gelatin, will be administered 20 minutes prior to the beginning of the training. Nicotine lozenges are mint-flavored "mini" lozenges, placebo lozenges are size-matched breath mints. Smokers in the Nicotine Group will receive a 4-mg lozenge. Plasma concentrations after this dose resemble the "nicotine boost" typically seen in dependent smokers by smoking a single cigarette (~1 ng/ml). Non-smokers in the Nicotine Group will receive a 2-mg lozenge because 4 mg in nicotine-naïve individuals would likely result in low tolerability. Participants will be instructed not to eat or drink within 15 min prior to or while consuming their lozenge. Participants may perform the training sessions at the Maryland Psychiatric Research Center (MPRC), or, in a separate room, at their day program or inpatient unit if applicable (a research associate would visit daily with laptop, lozenge or assessment instruments). The lozenge would be administered by a local nurse or other medical professional if possible, else these sessions would be performed at the MPRC. Participants who are unable to come to the MPRC or day program to complete the training (e.g., because they work or live too far away) may perform the exercises at home if they have internet access and their clinician or study staff considers them capable of doing so reliably. The CO measurement would be omitted on home-training days, and participants would be given the questionnaire about how much they slept and how much caffeine or alcohol they consumed to complete by themselves at home. On the two weekly lozenge days, they would be scheduled to perform the training at the MPRC. Under select circumstances, when the patient is unable to come to the MPRC on those days, too, they would be instructed to take the lozenge at home, following doctor's orders. A study team member would call them at home and

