If you uploaded a separate research protocol document in the 'Research Protocol' page, cite the applicable section and page numbers from that document in the answer boxes below.

- 1 * Provide the rationale and sample size calculations for the proposed target population:

Statistical and power analyses: Hypothesis 1a (larger or faster improvement in Nicotine than Placebo Group): Assuming training effects are linear with time, we will conduct an intention to treat (ITT) analysis by fitting the mixed model regression for repeated measures OCM= time+ treatment+ treatment x time, with time as a continuous measure. The treatment x time interaction estimates the difference between treatment groups in OCM rate of change (slope). Although we will include subjects with partial data, the effect size detectable was estimated conservatively⁷⁸ by: $d = [2(z_a + z_b)2(1-r)/bnVar(t)]/2$, where d = (difference in slopes)/SD(OCM), r = within-subject correlation of OCM, $b=4$ visits per subject, n = number of completers per group, $Var(t)=0.185$ is the within-subject variance of the visit times, and $z_a=1.96$ and $z_b=0.84$ for two-sided $\alpha=0.05$ and power=0.80. With $n=20$ completers per group, $d=0.56$ (a medium effect size) will be detectable for $r=0.7$ consistent with the high ICC of the MCCB, the primary OCM. To explore differences in treatment effects between MCCB domains, we will employ the mixed model for repeated measures: T-score= domain+ treatment+ time+ interactions. In particular, the domain x treatment x time interaction assesses variation among domains in the magnitude of the treatment effects on change slopes in OCM scores. In secondary analyses to guide the design of future studies, we will fit a model in which time is treated as a categorical measure unconstrained by a linear fit to explore different learning scenarios such as a more rapid initial acquisition but similar ceiling. In this model, we will add week 14 data to examine Hypothesis 1b (persistence of improvements after training ends), comparing treatment groups on the difference between week 14 and 10. Other exploratory analyses: 1) Smoking status (smoker, never-smoker) is added as an exploratory between-subject factor. 2) A further regression will explore differences between treatment groups in two compliance measures, the cumulative percentage of missed training sessions and lozenge administrations until each OCM time point. If treatment groups differ on compliance, we would include time-dependent compliance as a mediator of treatment effects. A descriptive analysis to support Hypothesis 1a will compare the percentage of participants in each group that achieves clinically significant improvement in MCCB composite scores (6 points from baseline adjusted for practice effects, see above) at each OCM time point.

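### Training-exercise progression is defined as a gain since the last visit but tested by its slope over time, so a steady nicotine benefit on this non-primary outcome could be missed

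*Combined protocol and SAP*

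**What the plan says.** Hypothesis 1a (Justification, Objective, & Research Design, item 1) predicts that nicotine "will accelerate the time course of performance enhancement on the MCCB and training exercise progression parameters". Item 2 of that section sets the schedule: "Outcome measures (OCMs) are assessed on Wednesdays in week 0 (day before training starts), weeks 4, 7 and 10", with a follow-up at week 14.

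Study Procedures, item 1, lists the MCCB as outcome (a). Outcome (b) is "The progression in training exercise parameters since the last outcome measurement time point (see below". The later text it points to describes two kinds of exercise. Some report parameter values after each session, and these are recorded on every training day. Others need a separate assessment, run with the outcome measurements.

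Sample Size and Data Analysis, item 1, gives one model for Hypothesis 1a, "OCM= time+ treatment+ treatment x time, with time as a continuous measure", on the premise "Assuming training effects are linear with time". It then says: "The treatment x time interaction estimates the difference between treatment groups in OCM rate of change (slope". The within-subject correlation used for power is described as "consistent with the high ICC of the MCCB, the primary OCM". No separate Hypothesis 1a model is given for outcome (b), and item 2, which asks for the analysis plan, refers back to item 1. A secondary model treats time as categorical and adds week 14.

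**The concern.** The slope model suits a level. If the MCCB score rises faster under nicotine, the two lines diverge and the interaction is the difference in rate. Outcome (b) is worded as an increment, so it is already a rate multiplied by the interval length. Its slope over time says whether learning speeds up or slows down, not how fast it is.

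Two features add to the problem. The intervals are unequal (4, 3 and 3 weeks), so gains fall after week 4 even when learning is steady. At week 0 there is no earlier outcome visit, so no gain exists there, and the plan does not say what is entered.

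At stake is one of the two measures whose time course Hypothesis 1a says nicotine will accelerate. An analyst following the text could find no interaction when nicotine does speed learning. An analyst who noticed would have to choose the scale and the week-0 handling after the data are in.

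**Working it through.** **The plan's own figure.** Inputs from Sample Size and Data Analysis, item 1: z values 1.96 and 0.84, r = 0.7, b = 4, n = 20 per group, Var(t) = 0.185. Reading the final term of the printed formula as a square root lost in conversion:

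d = sqrt[2(1.96 + 0.84)²(1 - 0.7) / (4 x 20 x 0.185)] = sqrt(4.704 / 14.8) = 0.564.

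This reproduces the stated 0.56. It concerns a level outcome, the MCCB.

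**Slope of the group difference.** Let improvement be positive and y be nicotine minus placebo. The interaction is the least-squares slope Σ(t - t̄)y / Σ(t - t̄)².

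- Weeks 0, 4, 7, 10: t̄ = 5.25, deviations -5.25, -1.25, 1.75, 4.75, sum of squares 54.75.
- Weeks 4, 7, 10: t̄ = 7, deviations -3, 0, 3, sum of squares 18.

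*Steady advantage of v per week (the plan's linear assumption).*

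| Outcome analysed | y | Slope per week |
|---|---|---|
| Level | 0, 4v, 7v, 10v | (-5 + 12.25 + 47.5)v / 54.75 = +v |
| Gain since last visit, weeks 4, 7, 10 | 4v, 3v, 3v | (-12 + 9)v / 18 = -0.167v |
| Gain per week, weeks 4, 7, 10 | v, v, v | 0 |
| Gain, week 0 entered as 0 | 0, 4v, 3v, 3v | (-5 + 5.25 + 14.25)v / 54.75 = +0.265v |

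The benefit has not vanished. It is in the average group difference, (4 + 3 + 3)v / 3 = 3.33v per interval.

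*Early gain.* Assume learning follows 1 - exp(-kt), with k = 0.20 under nicotine and 0.15 under placebo. These k values are illustrative; the documents give none. The level differences are 0, 0.0995, 0.1033 and 0.0878, so the gain differences are 0.0995, 0.0039 and -0.0156.

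| k, nicotine vs placebo | Level slope | Gain slope, weeks 4, 7, 10 | Gain slope, week 0 = 0 |
|---|---|---|---|
| 0.10 vs 0.075 | +0.010 | -0.010 | about 0 |
| 0.20 vs 0.15 | +0.009 | -0.019 | -0.0035 |
| 0.40 vs 0.30 | +0.002 | -0.022 | -0.006 |

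*Growing advantage.* Take a level difference of vt²/10, that is 0, 1.6v, 4.9v, 10v. The level slope is (-2 + 8.575 + 47.5)v / 54.75 = 0.988v. The gains are 1.6v, 3.3v and 5.1v, with slope (-4.8 + 15.3)v / 18 = +0.583v, or 28v / 54.75 = +0.511v with week 0 entered as 0. The sign is right.

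**Chance of detection.** In a simulation of 20,000 trials with 20 per group, a steady advantage of 0.56 SD over ten weeks was tested by t-tests on subject slopes. SD 1 and r = 0.7 are borrowed from the MCCB inputs, since none are given for the exercises.

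| Outcome analysed | Significant, right direction | Significant, wrong direction |
|---|---|---|
| Level | 64% | 0% |
| Gain, weeks 4, 7, 10 | 1.7% | 3.6% |
| Gain, week 0 = 0 | 10% | 0.4% |

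The level row is 64%, not 80%, because in units of ten weeks the divisor-4 variance of visits 0, 4, 7, 10 is 54.75 / 4 / 100 = 0.137, not 0.185. That is a separate matter; the comparison between rows is what counts here.

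**The case against.** Outcome (b) stands in a list of procedures and points to text describing recorded parameter values, which are levels. The analysis section also reads naturally for levels: it speaks of a rate of change and of groups reaching a similar ceiling. The investigators may well intend to analyse levels. That is fair, and it makes this a conflict of wording, not proof that a wrong analysis will be run. But the only definition of (b) as an outcome is an increment, and nothing in the analysis section overrides it.

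Three stronger readings are tempting, and the documents do not support them.

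- *The interaction must be zero or wrong-signed.* Under linearity that requires leaving week 0 out, yet the power formula counts four visits and week 0 is an outcome visit. With week 0 entered as 0 the linear case keeps its sign, at about a quarter of its size. A growing advantage keeps its sign either way.
- *The analysis would show harm.* Significant wrong-direction results occurred in 3.6% of simulated trials, close to the nominal 2.5% tail. The average group difference and the secondary categorical-time model would also show the gains. Neither is the named test, but both make a finding of harm unlikely.
- *The trial's main result is at risk.* The MCCB is the primary outcome and is a level. The within-session comparison for Hypothesis 2a is a separate analysis.

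**Conclusion.** The point holds for outcome (b) only. As worded, the outcome and the model do not fit together, and the week-0 value is undefined. Under the plan's linear assumption the named test recovers -0.17v, 0 or about +0.26v where +v is intended, depending on a choice that the plan leaves open. Early-gain curves can give the wrong sign; growing advantages give the right one. The practical consequence is loss of power on a non-primary outcome that Hypothesis 1a names. The primary MCCB analysis, d = 0.56 and the sample size stand.

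The steady-advantage results need only the visit weeks and the linear assumption. The curve and simulation figures rest on assumed learning rates and on SD and correlation values borrowed from the MCCB. The correction should be made, but it does not threaten the trial's main conclusion.

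**What to change.** In Study Procedures, item 1, define outcome (b) for the Hypothesis 1a model as the exercise parameter level at each outcome visit, or as cumulative change from a week-0 assessment made before the first training-phase lozenge, where one exists. Fit the model in Sample Size and Data Analysis to that, and keep interval gains as description only.

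Do not use the first training session as baseline. Week 0 is assessed on a Wednesday, the day before training starts, so the scheduled first session falls on a Thursday, which is a lozenge day. Its end-of-session value is after randomisation and under nicotine in one group.

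For exercises with no week-0 value, either fit the level at the available visits (under linearity 4v, 7v, 10v still gives +v) or test the average treatment difference in gain per week over weeks 4 to 7 and 7 to 10. Both options rely on linearity. With k = 0.20 vs 0.15 the level slope over weeks 4, 7 and 10 is 3(0.0878 - 0.0995) / 18 = -0.002, so a week-0 assessment is preferable where the software provides one.

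The cost is a few sentences, plus a list stating which value represents each of the eleven exercises and whether it exists at week 0. The values are already recorded or scheduled, so no visits are added. The wording should be fixed before unblinding.
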